Several stratified analyses will be conducted. PPSV23 is recommended for PLWH and feasibility data provided by Komodo suggest that one in four PWLH who received PCV13 during 2014-2015 also received PPSV23 within two years. Rather than censor or exclude

individuals who receive PPSV23, we will calculate PCV13 VE among PWLH who have/have not received PPSV23 before and during the study period.

Feasibility assessments from Komodo indicate that approximately 25% of PWLH have at least one CD4 cell count or percentage laboratory result available. Therefore, we will calculate PCV13 VE among the subset of PWLH who have a CD4 cell count during the baseline period or follow-up, and potentially stratify by CD4 category using each patient's lowest value during the study.

Additional VE stratifications by ART adherence during follow-up, year of HIV diagnosis, and age will be assessed for feasibility as well, as these affect patients' immune status and immune reconstitution. Due to possible waning of the VE and different lengths of follow-up by index year, VE stratification by year of HIV diagnosis will be restricted to the first 3 years of follow-up.

A sensitivity analysis will also be conducted. In this analysis, causes of pneumonia that are characteristic of HIV, for example pneumonia due to cytomegalovirus, mycobacteria, and fungi, will be excluded from our definition of all-cause pneumonia.

Residual confounding of our VE estimates due to inadequate control for health care seeking behavior and immune status in our analyses will be explored. To do so, we will employ a negative control exposure and a negative control outcome. Potential negative control exposures include vaccinations that are recommended for PLWH but would not be expected to have any protective effect against the pneumonia outcomes of interest. If residual confounding does not exist, the negative control vaccine would not have an effect on the pneumonia outcomes. However, if the analysis demonstrates that the negative control vaccine protects against these outcomes, this suggests the presence of residual confounding.

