**Table 5.2 Outcomes of Interest**

Outcome Type	Outcome	Definition
Primary outcomes	IPD	ICD-9-CM or ICD-10-CM codes listed in Appendix Table 7.4
	Pneumococcal pneumonia	ICD-9-CM or ICD-10-CM codes listed in Appendix Table 7.4
	All-cause pneumonia	ICD-9-CM or ICD-10-CM codes listed in Appendix Table 7.4
Secondary outcomes	Pneumococcal pneumonia or pneumonia with unspecified causes	ICD-9-CM or ICD-10-CM codes listed in Appendix Table 7.5
	Pneumonia with unspecified causes	ICD-9-CM or ICD-10-CM codes listed in Appendix Table 7.5
Sensitivity analysis outcome	All-cause pneumonia not associated with HIV	ICD-9-CM or ICD-10-CM codes listed in Appendix Table 7.6

For combination diagnosis codes, (e.g., bacteremia + pneumococcus) for diagnoses in an inpatient setting patients must have all codes within the same admission. The latest date of the combination of diagnoses will be used as the diagnosis date. For diagnoses in an outpatient setting patients must have all codes within the same date.

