### 5.3.3. Negative Controls

**Table 5.4 List of Negative Control Variables**

Variable	Operational Definition	Role	Time of Use
Recombinant zoster vaccine (RZV; Shingrix, GlaxoSmithKline)	NDC and CPT codes listed in Appendix Table 7.10	Negative control exposure	Follow-up
May include, but not limited to, candidiasis infection, all-cause diarrhea and accidental injury	ICD-9-CM and ICD-10-CM codes listed in Protocol Annex Table 4.1  Candidiasis infection: evidence of an antifungal treatment within 7 days of outpatient candidiasis ICD-9-CM or ICD-10-CM codes will be explored. NDC and CPT codes listed in Appendix Table 7.13	Negative control outcomes	Follow-up

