	482.39	Pneumonia due to other Streptococcus	J15.4	Pneumonia due to other streptococci
	482.4	Pneumonia due to Staphylococcus, unspecified	J15.20	Pneumonia due to staphylococcus, unspecified
	482.41	Methicillin susceptible pneumonia due to Staphylococcus aureus	J15.211	Pneumonia due to Methicillin susceptible Staphylococcus aureus
	482.42	Methicillin resistant pneumonia due to Staphylococcus aureus	J15.212	Pneumonia due to Methicillin resistant Staphylococcus aureus
	482.49	Other Staphylococcus pneumonia	J15.29	Pneumonia due to other staphylococcus
	482.81	Pneumonia due to anaerobes	J15.8	Pneumonia due to other specified bacteria

PFIZER CONFIDENTIAL

CT24-WI-GL03-RF03 3.0 *Non-Interventional Statistical Analysis Plan*  
for Secondary Data Collection Study  
Page 39 of 48

	482.82	Pneumonia due to escherichia coli [E. coli]	J15.5	Pneumonia due to Escherichia coli
	482.83	Pneumonia due to other gram-negative bacteria	J15.6	Pneumonia due to other aerobic Gram-negative bacteria
	482.84	Pneumonia due to Legionnaires' disease	A48.1	Legionnaires' disease
	482.89	Pneumonia due to other specified bacteria	J15.8	Pneumonia due to other specified bacteria
	482.9	Bacterial pneumonia, unspecified	J15.9	Unspecified bacterial pneumonia
	483	Pneumonia due to mycoplasma pneumoniae	J15.7	Pneumonia due to Mycoplasma pneumoniae
	483.1	Pneumonia due to chlamydia	J16.0	Chlamydial pneumonia
	483.8	Pneumonia due to other specified organism	J16.8	Pneumonia due to other specified infectious organisms
	484.1	Pneumonia in cytomegalic inclusion disease	B25.0	Cytomegaloviral pneumonitis
	484.3	Pneumonia in whooping cough	A37.91 A37.01 A37.11 A37.81	Whooping cough, unspecified species with pneumonia Whooping cough due to Bordetella pertussis with pneumonia Whooping cough due to Bordetella parapertussis with pneumonia Whooping cough due to other Bordetella species with pneumonia
	484.5	Pneumonia in anthrax	A22.1	Pulmonary anthrax
	484.6	Pneumonia in aspergillosis	B44.0	Invasive pulmonary aspergillosis

	484.7	Pneumonia in other systemic mycoses	J17	Pneumonia in diseases classified elsewhere
	484.8	Pneumonia in other infectious diseases classified elsewhere	J17 B77.81	Pneumonia in diseases classified elsewhere Ascariasis pneumonia
	485	Bronchopneumonia, organism unspecified	J18.0	Bronchopneumonia, unspecified organism
	486	Pneumonia, organism unspecified	J18.8 J18.9	Other pneumonia, unspecified organism Pneumonia, unspecified organism

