	510.x + 041.2	Empyema + pneumococcus		
	510 + 041.2	Empyema with fistula + pneumococcus	J86.0 + B95.3	Pyothorax with fistula + Streptococcus pneumoniae

	510.9 + 041.2	Empyema without mention of fistula + pneumococcus	J86.9 + B95.3	Pyothorax without fistula + Streptococcus pneumoniae
Pneumonia with unspecified causes	480-486 487.0			Viral, bacterial, unspecified pneumonia
	480.9	Viral pneumonia, unspecified	J12.9	Viral pneumonia, unspecified
	482.9	Bacterial pneumonia, unspecified	J15.9	Unspecified bacterial pneumonia
	485	Bronchopneumonia, organism unspecified	J18.0	Bronchopneumonia, unspecified organism
	486	Pneumonia, organism unspecified	J18.8 J18.9	Other pneumonia, unspecified organism Pneumonia, unspecified organism

Table 7.6 Diagnosis Codes for Identifying All-Cause Pneumonia not due to HIV

Condition	ICD-9-CM		ICD-10-CM	
	Codes	Description	Codes	Description
All-Cause	480-486 487.0			Viral, bacterial, unspecified pneumonia
	480	Pneumonia due to adenovirus	J12.0	Adenoviral pneumonia
	480.1	Pneumonia due to respiratory syncytial virus	J12.1	Respiratory syncytial virus pneumonia
	480.2	Pneumonia due to parainfluenza virus	J12.2	Parainfluenza virus pneumonia

	480.3	Pneumonia due to SARS-associated coronavirus	J12.81 J12.82	Pneumonia due to SARS-associated coronavirus Pneumonia due to coronavirus disease 2019
	480.8	Pneumonia due to other virus not elsewhere classified	J12.3 J12.89	Human metapneumovirus pneumonia Other viral pneumonia
	480.9	Viral pneumonia, unspecified	J12.9	Viral pneumonia, unspecified
	481	Pneumococcal pneumonia [Streptococcus pneumoniae pneumonia]	J18.1 J13	Lobar pneumonia, unspecified organism Pneumonia due to Streptococcus pneumoniae
	482	Pneumonia due to Klebsiella pneumoniae	J15.0	Pneumonia due to Klebsiella pneumoniae
	482.1	Pneumonia due to Pseudomonas	J15.1	Pneumonia due to Pseudomonas
	482.2	Pneumonia due to Hemophilus influenzae [H. influenzae]	J14	Pneumonia due to Hemophilus influenzae
	482.3	Pneumonia due to Streptococcus, unspecified	J15.4	Pneumonia due to other streptococci
	482.31	Pneumonia due to Streptococcus, group A	J15.4	Pneumonia due to other streptococci
	482.32	Pneumonia due to Streptococcus, group B	J15.3	Pneumonia due to streptococcus, group B
	482.39	Pneumonia due to other Streptococcus	J15.4	Pneumonia due to other streptococci
	482.4	Pneumonia due to Staphylococcus, unspecified	J15.20	Pneumonia due to staphylococcus, unspecified

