	482.41	Methicillin susceptible pneumonia due to Staphylococcus aureus	J15.211	Pneumonia due to Methicillin susceptible Staphylococcus aureus
	482.42	Methicillin resistant pneumonia due to Staphylococcus aureus	J15.212	Pneumonia due to Methicillin resistant Staphylococcus aureus
	482.49	Other Staphylococcus pneumonia	J15.29	Pneumonia due to other staphylococcus
	482.81	Pneumonia due to anaerobes	J15.8	Pneumonia due to other specified bacteria
	482.82	Pneumonia due to escherichia coli [ E. coli ]	J15.5	Pneumonia due to Escherichia coli
	482.83	Pneumonia due to other gram-negative bacteria	J15.6	Pneumonia due to other aerobic Gram-negative bacteria
	482.84	Pneumonia due to Legionnaires' disease	A48.1	Legionnaires' disease
	482.89	Pneumonia due to other specified bacteria	J15.8	Pneumonia due to other specified bacteria
	482.9	Bacterial pneumonia, unspecified	J15.9	Unspecified bacterial pneumonia
	483.1	Pneumonia due to chlamydia	J16.0	Chlamydial pneumonia
	483.8	Pneumonia due to other specified organism	J16.8	Pneumonia due to other specified infectious organisms
	484.3	Pneumonia in whooping cough	A37.91 A37.01 A37.11 A37.81	Whooping cough, unspecified species with pneumonia Whooping cough due to Bordetella pertussis with pneumonia Whooping cough due to Bordetella parapertussis with pneumonia Whooping cough due to other Bordetella species with pneumonia

	484.5	Pneumonia in anthrax	A22.1	Pulmonary anthrax
			J17	Pneumonia in diseases classified elsewhere
484.8	Pneumonia in other infectious diseases classified elsewhere	J17 B77.81		Pneumonia in diseases classified elsewhere Ascariasis pneumonia
485	Bronchopneumonia, organism unspecified	J18.0		Bronchopneumonia, unspecified organism
486	Pneumonia, organism unspecified	J18.8 J18.9		Other pneumonia, unspecified organism Pneumonia, unspecified organism
487	Influenza with pneumonia	J10.00 J10.08 J11.00 J11.08 J12.9		Influenza due to other identified influenza virus with unspecified type of pneumonia Influenza due to other identified influenza virus with other specified pneumonia Influenza due to unidentified influenza virus with unspecified type of pneumonia Influenza due to unidentified influenza virus with specified pneumonia Viral pneumonia, unspecified
510.x				Empyema
510	Empyema with fistula	J86.0		Pyothorax with fistula
510.9	Empyema without mention of fistula	J86.9		Pyothorax without fistula

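### The code list for the sensitivity outcome does not carry out its own exclusion rule (J17 stays when 484.7 goes), and the HIV-characteristic pneumonias it removes could serve as one more negative control outcome

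*SAP*

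**What the plan says.** Protocol 9.7 plans one sensitivity analysis, in which "causes of pneumonia that are characteristic of HIV, for example pneumonia due to cytomegalovirus, mycobacteria, and fungi, will be excluded" from the definition of all-cause pneumonia. SAP Table 5.2 lists the result as a single outcome, "All-cause pneumonia not associated with HIV", defined by Table 7.6, "Diagnosis Codes for Identifying All-Cause Pneumonia not due to HIV" (Protocol Appendix Table 11 is the same list). The full all-cause list is SAP Table 7.4.

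Residual confounding is treated separately, in SAP 5.3.3, 5.8.8 and 5.8.12. Recombinant zoster vaccine is the negative control exposure. Candidiasis is proposed as a probe for immune status, because CD4 values are missing for most patients. The list of negative control outcomes is open: "May include, but not limited to, candidiasis infection, all-cause diarrhea and accidental injury". SAP 5.8.12 specifies crude and weighted effectiveness models for PCV13 on candidiasis, treats a weighted 95% CI that excludes 0% as a sign of residual confounding, and allows the main results to be corrected for bias found through the negative control outcome.

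**The concern.** There are two matters.

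First, the sensitivity outcome should apply one rule across the whole study period. A code deleted in ICD-9 and kept in ICD-10 makes the outcome depend on calendar time, and leaves in it some of the fungal pneumonia it is said to exclude.

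Second, Pneumocystis, cytomegalovirus and aspergillus pneumonia are not plausibly prevented by PCV13, depend on immune status, and are pneumonia diagnoses like the main outcomes. That is what SAP 5.8.8 asks of a negative control outcome. Their codes are already listed, yet no effectiveness estimate against them is planned. Because the main results may be corrected using a negative control outcome, how closely that control shares their confounding bears on the corrected estimate.

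**Working it through.** **Step 1. The two code lists side by side** (SAP Tables 7.4 and 7.6; Protocol Appendix Tables 4 and 11 agree).

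| Cause | Table 7.4 | Table 7.6 |
|---|---|---|
| Pneumocystosis | 136.3 / B59 | both removed |
| "Cytomegaloviral pneumonitis" | 484.1 / B25.0 | both removed |
| Aspergillosis | 484.6 / B44.0 | both removed |
| "Pneumonia in other systemic mycoses" | 484.7 / J17 | 484.7 removed, J17 kept in a row with no ICD-9 code |
| Other infectious diseases | 484.8 / J17, B77.81 | all kept |
| Mycoplasma | 483 / J15.7 | both removed |
| Header range | 480-486, 487.0 | kept |

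J17 is labelled "Pneumonia in diseases classified elsewhere". It is the partner of both 484.7 (to be excluded) and 484.8 (to be kept). Systemic-mycosis pneumonia is therefore dropped under ICD-9 and kept under ICD-10. Deleting the emptied row alone would change nothing, because J17 is still counted beside 484.8. The header range, if programmed literally, would bring back 484.1, 484.6 and 484.7 (and 483). No code in Table 7.4 is labelled mycobacterial.

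**Step 2. Reproduce the plan's precision.** Protocol Table 3 gives, for VE 15%, 97 months and 4% censoring, 38,176 events and a 95% CI of 13% to 17%. Use SE(log HR) = 1/√(d·p·(1−p)), with d events and p the effective vaccinated share.
- p = 0.32 (share ever vaccinated, Protocol 9.5): SE = 0.0110, CI 13.2% to 16.8%.
- p = 0.16 (back-solved from the IPD interval of 11% to 33% on 1,452 events, Protocol Table 2): SE = 0.0140, CI 12.6% to 17.3%.

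Both round to the stated figure. The cautious p = 0.16 is used below.

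**Step 3. What comparing VE with and without the removed codes can show.** Let f be the removed share of events. The documents do not give it. As an approximation, overall HR = f·HR_removed + (1−f)·HR_retained. Hold overall VE at 15% and solve for the retained set:

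| HR in removed causes | f = 1% | 5% | 10% | 20% |
|---|---|---|---|---|
| 0.85 (equal confounding) | 15.0% | 15.0% | 15.0% | 15.0% |
| 0.70 (stronger confounding) | 14.8% | 14.2% | 13.3% | 11.3% |
| 0.50 (stronger still) | 14.6% | 13.2% | 11.1% | 6.2% |
| 1.00 (real vaccine effect) | 15.2% | 15.8% | 16.7% | 18.8% |

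The retained-set CI is about 12.5% to 17.5%. At f of 5% or less every scenario lies inside it; at 10% to 20% the estimate can move visibly.

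**Step 4. What analysing the removed codes on their own would show.** Events = f × 38,176. Power = Φ(|ln 0.85|/SE − 1.96), with |ln 0.85| = 0.1625.

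| f | Events | SE | 95% CI if VE = 0% | 95% CI if spurious VE = 15% | Power to flag HR 0.85 |
|---|---|---|---|---|---|
| 1% | 382 | 0.140 | −32% to 24% | −12% to 35% | 21% |
| 2% | 764 | 0.099 | −21% to 18% | −3% to 30% | 38% |
| 5% | 1,909 | 0.062 | −13% to 12% | 4% to 25% | 74% |
| 10% | 3,818 | 0.044 | −9% to 8% | 7% to 22% | 96% |

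These are favourable figures: longest follow-up, lower censoring, no loss from weighting. At 36 months, Protocol Table 2 (3% to 37% on 817 events) gives SE·√events of about 3.15. With 5% of 23,119 = 1,156 events, SE is 3.15/√1,156 = 0.093 and the CI around VE 15% is about −2% to 29%, which would not be flagged.

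**The case against.** The exclusion is an outcome-definition analysis, and neither document offers it as a check on confounding. The check is elsewhere, and it already includes an immune-status control chosen because it is more common, a negative control exposure, a decision rule and an open list to which these pneumonias could be added without changing the plan. All of this stands, and it limits the second part to an improvement.

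On coding, J17 is non-specific, so keeping it may be deliberate, to avoid losing 484.8-type events. But a row with no ICD-9 partner, present in both documents, does not read as a stated choice. The header range may be only a label: Table 7.5 carries the same range above its short list of unspecified causes, where a literal reading would make no sense. That is likely, but a programmer should not have to guess.

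A reader might infer that the removed pneumonias are discarded, and that a VE produced wholly by immune-status confounding would pass through the plan unchanged. The documents do not support this. The codes stay in the primary all-cause outcome. The sensitivity estimate is exactly unchanged only if confounding is equally strong in removed and retained causes (Step 3). And confounding is tested by other planned analyses.

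**Conclusion.** Two limited points hold.

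- **Code list.** Table 7.6 and Protocol Table 11 do not carry out the Protocol 9.7 rule: J17 is kept without its deleted partner, a header range is ambiguous, and Mycoplasma is removed where the protocol speaks of mycobacteria. This is a matter of text and needs no assumption. The number of events affected cannot be derived from the documents; it is probably small, and the listed primary outcomes are untouched.
- **Unused control.** The removed HIV-characteristic pneumonias fit the SAP's own description of a negative control outcome and would complement candidiasis. Their value depends on a share of events that is not given. At an assumed 5%, power to flag a spurious HR of 0.85 is about 74% before weighting; at 1% to 2% it is 21% to 38%. A null result would reassure only if its CI were narrow, and it should not be claimed that this outcome would settle the question.

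The change is worth making because it is cheap and addresses the bias that the sponsor itself identifies.

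**What to change.** 1. **SAP Table 7.6 and Protocol Appendix Table 11.** Delete the J17 row emptied of 484.7. Count J17 beside 484.8 only when the same claim or admission carries no mycosis code, and give that code list; the combination-code rule in SAP 5.3.1 (same admission, or same date for outpatients) could serve. Replace the 480-486 header range with the listed codes. State whether Mycoplasma, mycobacteria or both are meant, and make the protocol text and the tables agree.
2. **SAP Table 5.4 and 5.8.12.** Add a negative control outcome, HIV-characteristic pneumonia: 136.3/B59, 484.1/B25.0, 484.6/B44.0, and 484.7 or J17 with a mycosis code. Fit the same weighted Cox-MSM. In that run, remove these codes from the follow-up opportunistic-infection covariate, as Table 5.3 already does for Pneumocystis and candidiasis. Report the estimate, its CI and the event count beside candidiasis.

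Cost: wording in both documents, a short mycosis code list, and one more run of existing code. Downsides: probably fewer events than candidiasis, and some bacterial pneumonia may be miscoded as HIV-type, which would make the control slightly responsive to PCV13. Both should be stated with the result.

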**Table 7.9 National Drug Codes and CPT® Codes for Identifying PPSV23 Vaccination**

Code	Type	Description
90732	CPT	Pneumovax 23
00006473900	NDC	Pneumovax 23
00006473901	NDC	Pneumovax 23
00006473950	NDC	Pneumovax 23
00006474100	NDC	Pneumovax 23
00006483701	NDC	Pneumovax 23
00006483702	NDC	Pneumovax 23
00006483703	NDC	Pneumovax 23
00006489400	NDC	Pneumovax 23
00006489400	NDC	Pneumovax 23
00006494300	NDC	Pneumovax 23
00006494301	NDC	Pneumovax 23
00247040201	NDC	Pneumovax 23
50090145200	NDC	Pneumovax 23
50090145209	NDC	Pneumovax 23
54569141200	NDC	Pneumovax 23
54569653800	NDC	Pneumovax 23
54868333901	NDC	Pneumovax 23
54868333909	NDC	Pneumovax 23
54868432000	NDC	Pneumovax 23
54868432009	NDC	Pneumovax 23
55045354202	NDC	Pneumovax 23
00005230931	NDC	Pnu-Imune 23
00005230933	NDC	Pnu-Imune 23
54868070700	NDC	Pnu-Imune 23

**Table 7.10 National Drug Codes and CPT® Codes for Identifying Recombinant Zoster  
Vaccination**

Code	Type	Description
58160082801	NDC	Shingrix
58160082803	NDC	Shingrix
50090514700	NDC	Shingrix
58160081912	NDC	Shingrix
58160082311	NDC	Shingrix

50090337200	NDC	Shingrix
90750	CPT	Zoster Vaccine Recombinant, Adjuvanted, Suspension for Intramuscular Injection

**Table 7.11 CPT® Codes to Identify CD4 Laboratory Tests**

Code	Type	Description
86361	CPT	Absolute CD4 count
86360	CPT	Absolute CD4 and CD8 counts with ratio

**Table 7.12 CPT® Codes to identify Viral Load Laboratory Tests**

Code	Type	Description
87534	CPT	Infectious agent detection by nucleic acid (DNA or RNA); HIV-1, direct probe technique
87535	CPT	Infectious agent detection by nucleic acid (DNA or RNA); HIV-1, amplified probe technique
87536	CPT	Infectious agent detection by nucleic acid (DNA or RNA); HIV-1, quantification

